## **8.0                   Subject Disposition**

The number of subjects in each of the following categories will be summarized. The subsequently described analyses will be provided by country as well as by investigator and overall. Additionally, tables will be stratified by the parent study, Study M10-877/M10-880:

- Subjects who received at least one dose of study medication (safety set)
- Subjects who received at least one dose of study medication (ITT set)
- Subjects who completed (safety set)
- Subjects who prematurely discontinued (safety set)
- Subjects who are ongoing (safety set, in case of an interim analysis)

The number and percentages of subjects by parent study, Study M10-877/M10-880, and treatment in the parent study will be presented overall for the safety set.

The number and percentage of subjects who prematurely discontinued study drug during the study will be summarized by reason overall for the safety set.

The number and percentage of subjects with protocol deviations will be presented overall for the safety set.

The number and percentage of subjects per visit will be presented overall for the safety set.

## **9.0 Study Drug Exposure and Compliance**

Exposure to adalimumab in days (d) will be defined as follows:

Treatment exposure (days)

- = date of last dose of adalimumab in Study M11-327
- date of first dose of adalimumab in Study M11-327
- + 14 (days)

In addition, the total amount of exposure from first adalimumab dose in Study M10-877/M10-880 will be calculated as follows:

Treatment exposure (days)

- = date of last dose of adalimumab in Study M11-327
- date of first dose of adalimumab in Study M10-877/M10-880 or Study M11-327
- + 14 (days)

Exposure will be presented in weeks.

Exposure will be summarized by number of subjects, mean, standard deviation, minimum, first quartile, median, third quartile and maximum in the safety set. In addition, exposure

will be categorized and counts will be given for the number of subjects in the respective interval.

Treatment compliance (%) is defined as the number of adalimumab injections received divided by the number of injections planned in Study M11-327. Tabulations for treatment compliance will display the number of observations, mean, standard deviation, minimum, median and maximum.

## **10.0 Efficacy Analysis**

### **10.1 General Considerations**

The subsequently described analyses will be provided in the ITT set. All statistical analyses will be descriptive. Results will be stratified between subjects who entered into the study with active versus inactive uveitis. For subjects who had inactive and subjects who had active uveitis when they entered the study, the efficacy analyses will start at Baseline of Study M11-327. Results will also be provided overall except for efficacy variables defined differently for subjects entering Study M11-327 with active and inactive uveitis.

### **10.2 Efficacy Variables**

The following efficacy variables will be analyzed:

- Proportion of subjects with no active lesions in both eyes at each study time point.
- Proportion of subjects at each study time point with no new active, inflammatory chorioretinal or inflammatory retinal vascular lesion in both eyes relative to Baseline for subjects who had inactive uveitis when they entered the study and to Week 8 for subjects who had active uveitis when they entered the study.
- AC cell grade left/right eye and mean of both eyes at each study time point.
- Proportion of subjects at each study time point with a Grade  $\leq 0.5+$  in AC cells in both eyes on Slit Lamp Exam, according to SUN criteria.

- VH grades left/right eye and mean of both eyes at each study time point.
- Proportion of subjects at each study time point with a Grade  $\leq 0.5+$  in vitreous haze in both eyes on indirect ophthalmoscopy, according to NEI/SUN criteria.
- Proportion of subjects at each study time point with VH  $\leq 0.5$  and AC  $\leq 0.5$ .
- Proportion of subjects at each study time point with new lesions, AC  $\geq 2$  or VH  $\geq 2$ .
- Proportion of subjects at each study time point in quiescence defined as no active lesions, AC  $\leq 0.5$  and VH  $\leq 0.5$ .
- Proportion of subjects who experienced a uveitis flare (defined as no quiescence) during the study and who did or did not discontinue from the study due to the flare.
- LogMAR Best corrected visual acuity (BCVA) left/right eye and mean of both eyes at each study time point.
- Proportion of subjects at each study time point without a worsening of BCVA by  $\geq 15$  letters on the Early Treatment Diabetic Retinopathy Study (ETDRS) in both eyes relative to Baseline for subjects who had inactive uveitis when they entered the study and to Week 8 for subjects who had active uveitis when they entered the study.
- Proportion of subjects who started IMMs in Study M11-327.
- Proportion of subjects on/off IMMs at each study time point only in subjects on IMMs at baseline of Study M11-327.
- Proportion of subjects at each study time point achieving a  $\geq 50\%$  reduction in immunosuppression load relative to Baseline for subjects who had inactive uveitis when they entered the study and to Week 8 for subjects who had active uveitis when they entered the study.
- Change in dose of IMM at each study time point relative to baseline for subjects who had inactive uveitis when they entered the study and to Week 8 for subjects who had active uveitis when they entered the study only in subjects on IMMs at baseline/Week 8 of Study M11-327.
- Proportion of subjects who started systemic CS in Study M11-327.
- Systemic CS dose at each study time point.
- Proportion of subjects at each study time point with

- Systemic CS dose = 0 mg/day
- Systemic CS dose > 0 to  $\leq$  5 mg/day
- Systemic CS dose > 5 to  $\leq$  7.5 mg/day
- Systemic CS dose > 7.5 to  $\leq$  10 mg/day
- Systemic CS dose > 10 to  $\leq$  20 mg/day
- Systemic CS dose > 20 mg/day
- Percent change in systemic CS dose at each study time point relative to baseline only in subjects on CS at baseline.
- Proportion of subjects in steroid-free quiescence at each study time point.
- Proportion of subjects in quiescence and for subjects without quiescence the proportion of subjects
  - with/without a change in concomitant medication (topical/systemic corticosteroids, immunosuppressants) within 5 days after non-quiescence and with/without quiescence at the next visit (at least 8 Weeks after non-quiescence)
  - with premature discontinuation
- OCT evidence of macular edema in at least one eye at each study time point.
- Central retinal thickness left/right eye and mean of both eyes at each study time point by OCT machine.
- Percent change in central retinal thickness (1 mm subfield) in each eye at each study time point relative to Baseline for subjects who had inactive uveitis when they entered the study and to Week 8 for subjects who had active uveitis when they entered the study.
- Change in NEI Visual Functioning Questionnaire (VFQ-25) score at each study time point relative to Baseline for subjects who had inactive uveitis when they entered the study and to Week 8 for subjects who had active uveitis when they entered the study.

For analysis of central retinal thickness, the central retinal thickness measured by the investigator will be used. Changes and percent changes in central retinal thickness may only be calculated for measurements from the same machine. Central retinal thickness

will be analyzed excluding patients with macular hole and/or rhegmatogenous retinal detachment affecting the macular.

Immunosuppression load will be assessed according to the article by Nussenblatt et al. (2005). The below grading scheme will be used to accommodate the simultaneous use of multiple agents and provide a combined, single numeric score for the total immunosuppression load per unit body weight per day at each visit. For patients receiving multiple medications, the sum of the grading scores for each drug will be used to calculate a total immunosuppression score at each visit.

Medication	Immunosuppression Grade Based on Dose in mg/kg/day (or per Week if Dosed Weekly)							
	0	1	2	3	4	5	6	7
Prednisone	0	< 0.15	0.15 – 0.30	0.31 – 0.45	0.46 – 0.60	0.61 – 0.75	0.76 – 0.90	0.91 – 1.05
Cyclosporine	0	< 0.75	0.75 – 1.50	1.51 – 2.25	2.26 – 3.00	3.01 – 3.75	3.76 – 4.50	4.51 – 5.25
Azathioprine	0	< 0.25	0.25 – 0.50	0.51 – 0.75	0.76 – 1.00	1.01 – 1.25	1.26 – 1.50	1.51 – 1.75
Mycophenolate	0	< 10	10 – 20	21 – 30	31 – 40	41 – 50	51 – 60	> 60
Methotrexate	0	< 0.05	0.05 – 0.10	0.11 – 0.15	0.16 – 0.20	0.21 – 0.25	0.26 – 0.30	0.31 – 0.35
Cyclophosphamide	0	< 0.25	0.25 – 0.50	0.51 – 0.75	0.76 – 1.00	1.01 – 1.25	1.26 – 1.50	1.51 – 1.75
Chlorambucil	0	< 0.025	0.025 – 0.050	0.051 – 0.075	0.076 – 0.100	0.101 – 0.125	0.126 – 0.150	0.151 – 0.175

Note: Dose ranges are for the average in mg/kg/day, except for weekly doses of methotrexate, which are measured as mg/kg/week

The efficacy variables will be analyzed as follows.

Descriptive statistics for quantitative variables will include the number of observations, mean, standard deviation, minimum, first quartile, median, third quartile, and maximum for values at each visit, changes from Baseline/Week 8 to each visit thereafter and change from Baseline/Week 8 to Final/Early Termination Visit for continuous variables. In addition, for central retinal thickness percent change from Baseline/Week 8 to each visit thereafter and percent change from Baseline/Week 8 to Final/Early Termination Visit will be analyzed. For central retinal thickness, values at each visit and changes will be analyzed by OCT machine, percent changes will be analyzed overall. 95% confidence intervals for means will be provided. Data will be analyzed by Last Observation Carried Forward (LOCF) and as observed. For as observed analyses, graphs will be generated for subjects with active vs. inactive uveitis at entry of Study M11-327 for:

- LogMAR Best corrected visual acuity (BCVA) (mean of both eyes) at each study time point.
- Systemic CS dose at each study time point.
- Central retinal thickness (mean of both eyes) at each study time point by OCT machine.

Categorical variables will be summarized by counts and percentages at each visit. 95% confidence intervals for proportions will be provided. Data will be analyzed by Non Responder Imputation (NRI) and as observed. For as observed analyses, graphs will be generated for subjects with active vs. inactive uveitis at entry of Study M11-327 for:

- Proportion of subjects with no active lesions in both eyes at each study time point.
- Proportion of subjects at each study time point with a Grade  $\leq 0.5+$  in AC cells in both eyes on Slit Lamp Exam, according to SUN criteria.
- Proportion of subjects at each study time point with Grade  $\leq 0.5+$  in vitreous haze in both eyes on indirect ophthalmoscopy, according to NEI/SUN criteria.

- Proportion of subjects at each study time point in quiescence defined as no active lesions,  $AC \leq 0.5$  and  $VH \leq 0.5$ .
- Proportion of subjects with steroid-free quiescence at each study time point.
- OCT evidence of macular edema in at least one eye at each study time point.

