## **6.0 Analysis Conventions**

### **6.1 Definition of Baseline and Final Observation**

Baseline of the parent study, Study M10-877/M10-880, is defined as the last non-missing observation made on or prior to the first dose of study drug in Study M10-877/M10-880.

Baseline of Study M11-327 is defined as the last non-missing observation made on or prior to the first dose of study drug in Study M11-327.

The final observation is defined as the last non-missing observation available prior to last dose plus 70 days.

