### **10.3 Other Efficacy Variables**

The following other efficacy variables will be analyzed:

- Work Productivity and Activity Impairment, Questionnaire: Specific Health Problem Questionnaire (WPAI:SHP) and its components
- EuroQol Questionnaire (EQ-5D)
- Health Resource Utilization Questionnaire (HRU)

These other efficacy variables will be analyzed as follows.

For WPAI: SHP and EQ-5D, descriptive statistics will include the number of observations, mean, standard deviation, minimum, first quartile, median, third quartile, and maximum for values at each visit, changes from Baseline/Week 8 to each visit thereafter and change from Baseline/Week 8 to Final/Early Termination Visit for continuous variables. Data will be analyzed by Last Observation Carried Forward (LOCF) and as observed.

For HRU data, the individual cumulative number of utilizations per time under observation in Study M11-327 will be calculated in each category (i.e., unscheduled uveitis-related health care professional visits, emergency room visits, hospital admissions and the total number of days in hospital) as follows:

- Time under observation for a subject will be defined as "date of last visit with non-missing HRU – date of Baseline/Week 8 for subjects with inactive/active uveitis."
- The number of utilizations (documented starting at Week 2/Week 12 for subjects with inactive/active uveitis) will be summed up for each subject.

For cumulative HRU data, the ratio of the total number of utilizations (i.e., separately over all subjects with inactive and active uveitis) and the total time under observation (i.e., separately over all subjects with inactive and active uveitis) will be calculated across all subjects. HRU will be analyzed as observed only.

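### The SAP counts any non-quiescence during the study as a uveitis flare, with no earlier quiescent visit required, so residual entry disease in Treatment Failure entrants is scored as a flare

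*SAP*

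**What the plan says.** SAP 10.2 first defines a state at a visit: "Proportion of subjects at each study time point in quiescence defined as no active lesions", together with anterior chamber cells and vitreous haze each at 0.5 or lower. The next item builds the flare on that state: "Proportion of subjects who experienced a uveitis flare (defined as no quiescence) during the study and who did or did not discontinue", the split being whether the subject left because of the flare. No earlier quiescent visit, worsening step or starting week is attached.

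SAP 10.1 states, for active and inactive entrants alike, that "the efficacy analyses will start at Baseline of Study M11-327". It adds: "Results will also be provided overall except for efficacy variables defined differently for subjects entering Study M11-327 with active and inactive uveitis." The flare has one definition for both groups, so it is reported by stratum and overall.

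SAP 7.0 identifies active entrants as those who left the parent study for Treatment Failure, and protocol 5.1 says such subjects enter with active disease. Protocol 5.1 then takes two situations in turn: Treatment Failure entrants whose existing flare is not adequately controlled in the first 8 weeks, and all other subjects who flare on study in the investigator's judgement.

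**The concern.** A proportion of subjects with a flare on long-term treatment will be read as loss of disease control. As defined, it also contains disease that was present before the first open-label dose and had not yet settled. In the active stratum, and so in the overall figure, slow control, no control and relapse after control all score the same. The discontinuation split inherits the mixture: a subject who leaves because entry disease was never controlled sits in the same cell as one who became quiescent, lost control on drug and left.

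**Working it through.** The plan gives no flare rate, so there is no figure to reproduce. The check applies the rule to cases, looks for anything that limits it, and then works out direction and size.

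**Cases in the active stratum.**
- Not quiescent at Week 2 (Rx Days 2 to 22 in SAP 6.2) and Week 4 (Rx Days 23 to 43), quiescent at every later visit: flared, did not discontinue.
- Never quiescent, leaves because of it: flared, discontinued.
- Quiescent from Week 2, loses quiescence at Week 42 and leaves because of it: flared, discontinued.

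Only the third is a relapse.

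**Baseline.** SAP 6.1 says "Baseline of Study M11-327 is defined as the last non-missing observation made on or prior to the first dose of study drug". The SAP does not say whether that observation falls within the study for this variable. The point does not depend on it, because Weeks 2 and 4 are enough.

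**Limits elsewhere.** Nothing in SAP 6, 10.1, 10.2 or 10.4 restricts the variable to relapse. The SAP does allow for entry disease in other places. Several change variables in 10.2 are taken "relative to Baseline for subjects who had inactive uveitis when they entered the study and to Week 8 for subjects who had active uveitis". The health resource count in 10.3 is closer in kind, being an event count: "The number of utilizations (documented starting at Week 2/Week 12 for subjects with inactive/active uveitis) will be summed up for each subject."

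**Direction.** Anyone who loses quiescence after a quiescent visit has a non-quiescent visit, so is in the count as written. Slow-to-control and never-controlled entrants are added. On a common denominator the as-written proportion is therefore at least the relapse proportion.

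**Size, illustration only.** All inputs are assumed; none is in the documents. Baseline is not counted. Among active entrants, q is the share not quiescent at Baseline and still not at Week 2, u (at most q) the share never quiescent, and r the relapse risk once quiescent. With all active entrants as denominator:

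- As written: q + (1 − q)r
- Relapse: (1 − u)r
- Excess: q(1 − r) + ur

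For q = 50%, u = 15%, r = 20%: as written 0.5 + 0.5 × 0.2 = 0.60; relapse 0.85 × 0.2 = 0.17; excess 0.5 × 0.8 + 0.15 × 0.2 = 0.43.

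| r (u = 15%) | As written, q = 30 / 50 / 70% | Relapse |
|---|---|---|
| 10% | 37 / 55 / 73% | 8.5% |
| 20% | 44 / 60 / 76% | 17% |
| 40% | 58 / 70 / 82% | 34% |

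For the overall figure, let a be the active share, and assume that inactive entrants all start quiescent and have the same r. At q = 50%, u = 15%, r = 20% and a = 50%, as written is 0.5 × 0.60 + 0.5 × 0.20 = 40%, and relapse is 0.5 × 0.17 + 0.5 × 0.20 = 18.5%. At a = 30% the pair is 32% and 19.1%; at a = 70% it is 48% and 17.9%.

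Among ever-quiescent subjects only, relapse is r itself, here 20%. That figure has a different denominator and should not be subtracted from the 60%.

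**The case against.** The SAP never says that this variable measures relapse. Protocol 5.1 itself calls the entry disease of Treatment Failure entrants a flare, so counting it fits the protocol's vocabulary. Results are stratified, so no reader is left with the pooled figure alone. Quiescence is tabulated by visit, and another 10.2 item follows non-quiescent subjects through a prompt change of concomitant medication, quiescence at a next visit at least 8 weeks later, and premature discontinuation. The Week 8 comparison is partly unlike for like: new lesions and visual acuity loss are changes and need a reference visit, while cell grade, haze and quiescence are states and have none. Everything here is descriptive, in an open-label study whose primary objective is safety.

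Much of this stands, and it narrows the point. The vocabulary argument does not remove it: protocol 5.1 keeps entry disease apart from on-study flares in other subjects, and the SAP variable merges them. Stratification leaves the active stratum mixed. The by-visit tables and the follow-up item show part of the residual disease, but neither requires earlier quiescence, so neither gives relapse per subject.

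A reader might also infer that the inactive-stratum figure is sound. The documents do not establish that: SAP 7.0 defines the strata by Treatment Failure, not by quiescence, so inactive entrants who are non-quiescent at entry are affected in the same way.

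**Conclusion.** The point holds. The flare proportion as defined mixes uncontrolled entry disease with loss of control, in the active stratum and overall, and should be redefined. The direction is certain on a common denominator. The size is not: it depends on early control, relapse risk and the active share, none of which the documents give.

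Two stronger readings are tempting. A reader might infer that the active stratum is bound to show nearly 100% flares. That would need Baseline to be counted and every active entrant to be non-quiescent then, and the SAP states neither. A reader might also take the Baseline start in SAP 10.1, against the Week 8 start in protocol 8.1.4, as the cause. That mismatch is a separate matter. A Week 8 start would still count entry disease not yet controlled at Week 8, so it would not by itself turn the variable into relapse.

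No test, error rate or safety result is involved.

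**What to change.** In SAP 10.2, count a new flare only as non-quiescence at an observed visit after a documented quiescent visit. Baseline may serve as the quiescent visit but not as the flare visit. Report it by stratum and overall, with the existing split by discontinuation due to the flare. Report subjects who never reach quiescence separately, with the same split.

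State the denominator, for example subjects with a quiescent visit and at least one later observed visit. Give the number with a quiescent visit but no later one, so that the groups add up. State that imputed visits do not create a flare: SAP 6.3.1 sets missing binary values to non-response without saying how that applies here.

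The cost is the re-derivation of one descriptive variable, a smaller denominator, and an added row or two. No new data are needed, because protocol 5.3.1.1 has cells, haze and lesions examined at every visit.

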5.0 Investigational Plan

5.1 Overall Study Design and Plan: Description

This study is a Phase 3, open-label multicenter study designed to evaluate long-term safety and efficacy of adalimumab in adult subjects with non-infectious intermediate-, posterior-, or pan-uveitis who have either discontinued from Study M10-877 or Study M10-880 for having met "Treatment Failure" criteria or have successfully completed Study M10-877 or Study M10-880. Subjects who prematurely discontinue from Study M10-877 or Study M10-880 for reasons other than for Treatment Failure as defined in the parent protocol, will not be eligible for this study.

Figure 1. Study Schematic

* Visits will occur every 12 weeks following Week 66 until the end of the study (not to exceed 15 March 2018).

Subjects rolling over from Study M10-877 and Study M10-880 will be evaluated for entry into this study at the final or last visit in the parent study. Therefore, Study M11-327 Baseline (Week 0) visit will be performed on the same day as the Final/Early Termination visit in the parent studies. At this visit, after administering and obtaining the subject's consent, subjects will be evaluated to ensure they meet all inclusion criteria and none of the exclusion criteria listed in Section 5.2. If the Baseline visit occurs greater than (>) 14 days after the Final/Early Termination visit of the parent study, all procedures listed in the Baseline visit must be completed. The maximum amount of time allowed between the Final/Early Termination visit of the parent study and the Baseline visit of Study M11-327 is 28 days.

Starting at Baseline, all subjects will receive open-label adalimumab 40 mg dose eow SC regardless of treatment assignment in the randomized, double-masked Study M10-877 or Study M10-880.

As subjects who discontinue from Study M10-877 or Study M10-880 due to "Treatment Failure" will have active disease on study entry into Study M11-327, concomitant therapy with corticosteroids (oral or topical) and/or any one of the immunosuppressive therapies permitted in Study M10-877 and Study M10-880, will be allowed as necessary to control intraocular inflammation.

Subjects who successfully complete Study M10-877 or Study M10-880 and have inactive disease at time of entry into Study M11-327 may continue, taper and/or discontinue concomitant corticosteroids and/or immunosuppressive therapy which were permitted in Study M10-877 and Study M10-880 based on the investigator's clinical judgment.

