Subjects may be on only one of the allowed systemic immunosuppressants in addition to a systemic corticosteroid, at any timepoint.

Study visits will occur at Week 0, 2, 4, 8, 12, 18 and every 12 weeks thereafter. Efficacy assessments will be performed at every visit (Section 5.3.1). Both of the subject's eyes should be evaluated. **There will be no designated "study eye."**

Subjects who enter the study due to Treatment Failure in Study M10-877 or Study M10-880 and fail to achieve adequate control of their disease flare within the first 8 weeks may discontinue from the study.

Any other subject experiencing a uveitis flare during the study as determined by the investigator may discontinue from the study. Subjects may continue in the study, if it is determined by the investigator that the flare was triggered by a reduction or discontinuation in concomitant corticosteroid or systemic immunosuppressive therapy where further adjustment to the concomitant therapy may be warranted. Any subject continuing to have an active uveitis flare for 4 weeks or more should be discontinued from the study.

The site research staff will instruct and supervise subjects or a designee on proper injection technique at the scheduled visits. Subjects or a trained designee will administer adalimumab outside of clinic visits according to the specified dosing schedule.

An Independent Data Monitoring Committee (IDMC) will be established to independently monitor and assess data for Study M10-877, Study M10-880 and Study M11-327. The IDMC will be in effect until the end of both Study M10-877 and Study M10-880. At each committee meeting, the IDMC will undertake a comprehensive review and assessment of the cumulative safety data, which will include M11-327 study data.

Subjects may discontinue adalimumab treatment at any time during study participation. Subjects that end study participation early will have an Early Termination Visit. No study drug will be administered or injected at the final visit.

Safety data will be collected in the form of adverse events, physical examination, vital signs and laboratory tests throughout the treatment period and up to 70 days after the last injection in this study. All subjects will have a 70-day follow-up phone call or clinic visit to obtain follow-up information on any new or ongoing adverse events. The 70-day follow-up phone call will not be required for any subject that initiates commercial adalimumab after the end of study participation.

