A repeat ANA/Anti-ds-DNA would be warranted if a subject has clinical signs and symptoms suggestive of lupus. The Anti-ds-DNA antibody testing will be performed in case of a positive ANA result.

All samples will be sent to the central laboratory for processing.

Adverse Events

Adverse events will be assessed at every study visit from Baseline through the Final/Early Termination visit, and during the 70-day phone call or clinic visit (if applicable). A phone

call or routine clinic visit should occur approximately 70 days after last dose of study medication to obtain follow-up information on any ongoing or new adverse events (Section 6.0 and Appendix D).

Any ongoing adverse events at the time of the Termination visit in the previous Study M10-877 or Study M10-880 will be automatically transferred onto the Study M11-327 eCRF.

Concomitant Medication

All medications (including, but not limited to, prescription or over-the-counter medicines such as aspirin, antacids, vitamins, mineral supplements, and herbal preparations) used from the Baseline visit through the end of the study must be recorded on the appropriate eCRF. Any ongoing systemic or local therapy at the time of Termination visit in the previous study M10-877 or M10-880 will be automatically transferred onto the M11-327 eCRF.

Contact the AbbVie Medical Monitor identified in Section 6.1.5, if there are any questions regarding concomitant or prior therapy(ies).

Each vaccine administered to the subject should be listed as a concomitant medication on the Other Medications eCRF. Live vaccines may not be given concurrently while on study drug or for 70 days after the last dose of adalimumab.

Concomitant use of nutritional supplements should be recorded as concomitant medications (generic and/or brand name, dose [if known], frequency) on the Other Medications eCRF.

Dispense Study Drug

Study drug will be administered to subjects by study site medical staff, by himself/herself or by a designee (friend, family member or health care professional) throughout the study.

Subjects, a designated family member or friend, will be trained to administer study medication during the first visit or several times, if appropriate. This training must be documented in the subject's source document.

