5.6.3 Suitability of Subject Population

Subjects with uveitis who met the endpoint treatment failures or have successfully completed Study M10-877 or Study M10-880 may be eligible for this study. These subjects are candidates for systemic immunosuppressive therapy to allow reduction and/or discontinuation of corticosteroid therapy.

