8.1.4 Analysis of Efficacy

All statistical analyses will be descriptive. Results will be stratified between subjects who entered into the study with active versus inactive uveitis. For subjects who had active uveitis when they entered the study, the efficacy analyses will start at Week 8. For subjects who had inactive uveitis when they entered the study, the efficacy analyses will start at Week 0. Continuous variables will be summarized by the number of non-missing observations, mean, standard deviation, median, quartiles, minimum and maximum. Categorical variables will be summarized by counts and percentages.

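### SAP 10.2 measures percent change in corticosteroid dose from study entry even in Treatment Failure subjects, so tapering a rescue dose given by Day 1 is scored as a reduction

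*SAP*

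**What the plan says.** The variable is "Percent change in systemic CS dose at each study time point relative to baseline only in subjects on CS at baseline" (SAP 10.2). It has no separate reference for subjects who entered with active disease, whom SAP 7.0 defines as those who left the parent study for Treatment Failure.

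SAP 6.1 defines Study M11-327 baseline as "the last non-missing observation made on or prior to the first dose of study drug in Study M11-327". SAP 7.5 counts a drug begun on the first-dose day as a baseline medication, and the Week 0 window in SAP 6.2 ends on Rx Day 1.

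For Treatment Failure entrants, Protocol 5.1 says that corticosteroids and/or one permitted immunosuppressant "will be allowed as necessary to control intraocular inflammation". It also plans that the "Baseline (Week 0) visit will be performed on the same day as the Final/Early Termination visit in the parent studies", with a gap of at most 28 days allowed.

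Protocol 8.1.4 states: "For subjects who had active uveitis when they entered the study, the efficacy analyses will start at Week 8". SAP 10.1 instead starts the efficacy analyses at Study M11-327 baseline for both groups. It adds overall results for every variable whose definition does not differ by entry status.

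**The concern.** The visit at which failure is recorded is normally also the visit at which baseline is set. It is a natural day to start or raise steroids, and the plan then treats the raised dose as the starting point. A fall from a flare-rescue dose is expected as the rescue is withdrawn, whatever adalimumab does in the long term. In a single-arm open-label study nothing else in the design separates the two.

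At stake is the reading of one descriptive efficacy result. Protocol 5.6.3 calls these subjects "candidates for systemic immunosuppressive therapy to allow reduction and/or discontinuation of corticosteroid therapy", so a table showing a large percent fall in steroid dose would readily be read as steroid sparing.

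**Working it through.** The analyses are descriptive and the documents give no steroid doses, so there is no planned figure to reproduce. The check is a trace of definitions, followed by arithmetic on assumed doses.

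**1. What enters the reference.** By SAP 6.1 and 7.5, steroid treatment in place on Day 1 is baseline treatment. Rescue begun at the parent termination visit, or in the gap of up to 28 days before the first dose, is therefore in the denominator. Rescue begun on Day 2 is not.

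**2. How neighbouring variables are handled.** In SAP 10.2 the following use Baseline for inactive entrants and Week 8 for active entrants: new active lesions, BCVA worsening, immunosuppression load, immunosuppressant dose, percent change in retinal thickness, and VFQ-25. The carry-forward rule in SAP 6.3.2 likewise treats Week 8 as the active group's reference value. Percent change in steroid dose lacks that branch. Because its definition does not differ by entry status, SAP 10.1 also has it reported pooled.

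**3. Single subjects.** Score = 100 × (later dose − reference dose) / reference dose. All doses are assumed, in mg/day.

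| Before failure | Day 1 | Week 8 | Later | From Day 1 (current SAP) | From Week 8 | Change from pre-failure dose |
|---|---|---|---|---|---|---|
| 5 | 40 | 10 | 5 | (5−40)/40 = −87.5% | (5−10)/10 = −50.0% | 0 |
| 7.5 | 20 | 10 | 7.5 | (7.5−20)/20 = −62.5% | (7.5−10)/10 = −25.0% | 0 |
| 10 | 40 | 10 | 10 | (10−40)/40 = −75.0% | 0% | 0 |
| 5 | 40 | 15 | 10 | (10−40)/40 = −75.0% | (10−15)/15 = −33.3% | +5 |
| 5 | 5, rescue to 40 on Day 2 | 10 | 5 | 0% | −50.0% | 0 |

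The fourth subject ends on twice the pre-failure dose and still scores a 75% reduction. The first and last differ by one day in the start of rescue and score −87.5% and 0%. A subject off steroids before failure, started on Day 1 and later back to zero, scores −100%.

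**4. Group means.** Let f be the share of active steroid users rescued by Day 1, r their rescue dose and p the dose to which they return, equal to the pre-failure dose. Everyone else is unchanged. Mean = f × (p − r)/r.

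- f = 0.10, p = 7.5, r = 20: 0.10 × (−62.5%) = −6.25%
- f = 0.25, p = 5, r = 20: 0.25 × (−75%) = −18.75%
- f = 0.75, p = 5, r = 60: 0.75 × (−55/60) = −68.75%

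For the pooled result, multiply by the active share of steroid users, assumed to be 0.4 to 0.6. This gives 0.4 × (−6.25%) = −2.5% up to 0.6 × (−68.75%) = −41.25%.

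These values show direction and sensitivity. They are not estimates of what the trial will report.

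**The case against.** The strongest reply is that the plan already contains checks.

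- **Immunosuppression load.** It has prednisone in its grading table and is referenced to Week 8 for active entrants. This stands as a partial check. It is a combined multi-drug grade, so it does not replace the steroid result.
- **Other steroid outputs.** Dose by visit, dose categories and steroid-free quiescence show where a subject ends up without any reference dose. Results are split by entry status before they are pooled. This also stands, although none of these outputs shows the dose before failure.
- **The general rule in SAP 10.2.** Changes in continuous variables are taken from Baseline/Week 8, which may cover absolute change in steroid dose. Its percent-change rule names only retinal thickness, and the steroid bullet is specific, so this is an ambiguity to close.
- **Missing detail.** The bullet does not say which study's baseline it means, and no rule derives the Day 1 dose when two dose records meet on that day. SAP 6.1, 7.5 and 10.1 point to Study M11-327 with Day 1 included.
- **The pre-failure dose as the main reference.** Disease failed on that dose, so being quiescent on it later is a gain that this reference would score as zero. The point stands, and the pre-failure comparison is proposed only as support.

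A reader might go further and infer that steroid reduction is the trial's main efficacy message. The documents do not support that. Protocol 5.6.3 describes the population, the variable is not among those in Protocol 5.3.3, it was added in SAP Amendment 2, and the primary objective is safety. Nor can one infer that Day 1 rescue is hidden from the variables counting subjects who started a drug, because the SAP does not define starting.

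**Conclusion.** The point holds for Treatment Failure entrants whose steroids were started or raised on or before Day 1. For them the planned percent change counts withdrawal of rescue as dose reduction, and the pooled result carries this forward. The SAP departs here from the Week 8 convention it applies to its other change variables.

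The size cannot be determined from the documents. The illustrated −6% to −69% in active steroid users, and −2.5% to −41% pooled, rest on assumed doses, rescue shares and a full return to the pre-failure dose. A reader might take them as the expected bias, or conclude that any reported steroid reduction is spurious; neither follows. Rescue begun after Day 1 in a subject already on steroids appears as an increase until tapered, and in a subject not on steroids at baseline it falls outside the variable. No claim is made about the safety objective. The change is worth making because it is cheap and follows the plan's own convention.

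**What to change.** In SAP 10.2:

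1. Define percent change in systemic corticosteroid dose relative to Study M11-327 Baseline for inactive entrants and to Week 8 for active entrants, in subjects on corticosteroids at that reference. The variable then differs by entry status and is no longer pooled under SAP 10.1.
2. Keep the current percent change for active entrants as a row labelled *from entry dose, including any rescue*, by entry status only.
3. As a supportive row where parent-study medication records allow, show for active entrants the absolute change in mg/day from the dose on the day before the parent-study Final/Early Termination visit.

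The cost is one or two extra table rows, with no protocol amendment and no new data collection. The third item may need parent-study records. Protocol 5.3.1.1 transfers "Any ongoing systemic or local therapy at the time of Termination visit in the previous study", and a dose record that ended when the dose was raised at that visit might not carry over.

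There are downsides. The reported reduction may look smaller. The Week 8 reference removes the artefact only as far as rescue has been tapered by then. Subjects off steroids at Week 8 have no percent change, nor do those who left earlier; Protocol 5.1 says that Treatment Failure entrants who "fail to achieve adequate control of their disease flare within the first 8 weeks may discontinue from the study". Keeping the second and third rows leaves these subjects visible where their data exist.
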